## 7.5.2 Secondary Imaging Endpoint

To characterize the  $^{11}\text{C-BMS-986196}$  tracer signal, summary statistics will be provided for calculated SUV and  $V_T$  in the brain and presented by visit and each appropriate ROI for the Response-Evaluable 2 population (Parts A and B). As sensitivity analysis for the secondary imaging endpoint, the analysis may be repeated, if deemed appropriate, for the Per-Protocol 2 population (Parts A and B).

## 7.6 Safety

For the calculation of the changes from baseline, baseline will be defined as the last non-missing observation including unscheduled measurements recorded before the first dosing of study treatment.

Data collected from sampling at unscheduled visits or time-points at post-dose will be excluded from summary tables by visit or time-point.

#### 7.6.1 Deaths

All reported deaths after enrolment (i.e., participant has signed the informed consent) will be listed for the Enrolled population.

#### 7.6.2 Adverse Events

All AEs will be coded and grouped into Preferred Terms (PT) by System Organ Class (SOC), using the current version of the Medical Dictionary for Regulatory Activities (MedDRA).

Treatment-emergent adverse events (TEAEs) will be defined as any AEs that start on or after administration of study treatment and until 10 days after last dose of study treatment or date of last study visit, whichever is later.

Only TEAEs will be tabulated. Events will be assigned to the study treatment administered to the participant. For tabulating incidence of TEAEs, the proportion of participants having an TEAE will be calculated as the number of participants experiencing the event, divided by the total number of participants in the Safety population. TEAEs will be summarized by SOC, PT, treatment, and overall.

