Procedure	Visit 1 Day 1 ^a	Visit 2 (2 hrs to 6 days after Visit 1 tracer administration)	Safety Follow-up 3 days (± 1 day) after most recent PET Scan ^c /Early Termination ^d	Notes
Safety Assessments				
Weight Measurement	X	X		
Partial PE	X	X		PE must be done within 24 hrs of tracer administration. Symptom-based PE only.
12-Lead ECG	X	X		ECGs should be recorded after the participant has been supine for at least 5 min. ECG will be conducted prior to tracer administration and after completion of the PET scan. See Section 9.4.5.
Vital Signs	X	X		VS will be obtained before tracer administration, after PET scan completion, and prior to discharge on Visits 1 and 2. See Section 9.4.3.
Allen's Test		X		Normal result (in the arm that will be used for arterial line placement) must be documented prior to arterial line placement.
Hematology, Chemistry, Urinalysis	X	X		Participants are required to fast for at least 10 hrs prior to specimen collection. Specimens will be collected at least 1.5 hrs after the first tracer administration and at least 1.5 hours after the second tracer administration. See Section 9.4.6 for full list of clinical laboratory safety tests/assessments.
Pregnancy Test (WOCBP only)	X	X		Urine or serum test. Result must be confirmed as negative prior to tracer administration on Day 1.
Review of Emergency Contact Instructions	X	X		Prior to discharge on Visits 1 and 2.

Table 2-2: Imaging Procedural Outline for Part A (IM038010)

Procedure	Visit 1 Day 1 ^a	Visit 2 (2 hrs to 6 days after Visit 1 tracer administration) ^b	Safety Follow-up 3 days (± 1 day) after most recent PET Scan ^c /Early Termination ^d	Notes
Non-serious AE and SAE Assessments	X	X	X	All SAEs must be collected from the time of signing the consent until 10 days after the last tracer administration or the final visit, whichever is later. All AEs (SAEs and non-serious AEs) associated with SARS-CoV-2 infection must be collected from the date of participant's written consent. See Section 9.2.1.
Concomitant Medication Use	X	X	X	
Imaging Assessments and Subseq	uent Procedures			
Arterial Line Placement		X		Prior to tracer administration.
Venous Line Placement for Venous Blood Sampling (During Visit 2 PET Scan)		X		Prior to tracer administration (on the arm opposite to the tracer administration). Only in up to 2 participants (added to Part A after initiation of Part B) undergoing simultaneous arterial and venous blood sampling.

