Whole-body PET-CT Scan	X			Whole-body PET-CT scan is from apex to the upper-thigh level.
Cranial PET-CT Scan or PET-MRI Scan		X		PET-CT or PET-MRI is performed, depending on equipment availability. The cranial PET scan is performed after the whole-body PET-CT scan. If scans are performed on the same day, participants are allowed to have a light meal between the whole-body PET scan and the cranial PET scan.
Check Pressure Dressing, Hand and Finger Circulation		X		After arterial line placement, throughout the PET procedure, following removal of the arterial line, and before discharge

27

Table 2-2: Imaging Procedural Outline for Part A (IM038010)

Procedure	Visit 1 Day 1 ^a	Visit 2 (2 hrs to 6 days after Visit 1 tracer administration) ^b	Safety Follow-up 3 days (± 1 day) after most recent PET Scan ^c /Early Termination ^d	Notes
Radiotracer Administration				
Overnight and Post-dose Fasting	X	X		The night before tracer administration, participants will fast for at least 8.5 hrs before tracer administration and will remain fasted until at least 1.5 hrs after tracer administration.
				If 2 tracer administrations are performed on the same day, participants can have a light meal after the first tracer administration.
¹¹ C-BMS-986196 Tracer Administration	X ^a	X ^a		Tracer is administered by a slow IV bolus prior to the whole-body PET scan and again prior to the cranial PET scan.

Abbreviations: AE, adverse event; ECG, electrocardiogram; hr, hour; IV, intravenous; min, minute; PE, physical examination; PET, positron emission tomography; PET-CT, positron emission tomography - computed tomography; PET-MRI, positron emission tomography - magnetic resonance imaging; SAE, serious adverse event; SARS-CoV-2, severe acute respiratory syndrome coronavirus 2; VS, vital signs; WOCBP, women of childbearing potential.

Protocol Amendment No.: 05

^a Prior to initiation of Part B, all Part A participants undergo Visits 1 and 2. After initiation of Part B, up to 2 participants may be added to Part A, and will not undergo Visit 1, only Visit 2. For these participants only, Visit 2 will be regarded as Day 1.

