10.4.2 Primary Endpoint(s)

Table 10.4.2-1: Endpoints

Primary Endpoint	Description	Timeframe
Incidence, severity, seriousness, type of AEs. (Safety Population)	Incidence of AEs, SAEs, severe, type of AEs. AEs listed by frequency	Treatment emergent during the study
Incidence of clinically significant abnormal findings. (Safety Population)	Incidence of clinically significant abnormal findings in ECG, laboratory values, VS, physical examination	Treatment emergent during the study
Radiation dosimetry (Part A only). (Response-Evaluable 1 Population)	Organ absorbed dose and whole-body effective dose	After ¹¹ C-BMS-986196 tracer administration at Visit 1
Window of acquisition. (ResponseEvaluable 2 Population)	Time during which peak PET signal is detected	Part A Visit 2, and Part B Visit 1 and Visit 2 after ¹¹ C-BMS-986196 tracer administration
Test-Retest Repeatability (Part B only). (Response-Evaluable 3 Population)	Quantitative analysis of PET signal in CNS between 2 evaluable PET sessions	Visit 1 and Visit 2 after 11C-BMS-986196 tracer administration
% Free brain BTK relative to baseline (Part C only)	Proportion of free brain BTK at Visit 2 relative to Visit 1	Visit 1 and Visit 2

Abbreviations: AE, adverse event; CNS, central nervous system; ECG, electrocardiogram; PET, positron emission tomography; SAE, serious adverse event; VS, vital signs.

All recorded AEs will be listed according to system organ class and preferred term and tabulated by study part. ECGs as reported on the ECG CRF (including abnormality) will be reported separately. Vital signs as reported on the VS CRF will be reported separately. Physical examinations as recorded on the PE CRF will be reported separately. Clinical laboratory test results as reported on Lab CRF will be reported separately. Vital signs, ECGs, and laboratory test results will be summarized.

For test-retest repeatability in Part B, descriptive statistics will be reported by measurement. A scatter plot of test versus retest with the line of equality will be created. A plot of differences between retest and test versus the mean of the test and retest may also be constructed. The estimated limits of agreement will be also presented on this plot.

The proportion of free brain BTK relative to baseline will be summarized for Part C.

Descriptive statistics and plots may be provided for the other endpoints. Other details may be added in the SAP as appropriate.

Protocol Amendment No.: 05

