## 6.1 Study Periods

Study Day 1 will be defined as the day of first administration of tracer C-BMS-986196. The day before the first administration will be defined as Study Day -1, there is no Study Day 0.

For statistical analysis, the following analysis periods will be defined:

- Pre-treatment period: starts at signing of informed consent (ICF) and lasts up to first dosing date/time on Study Day 1.
- On treatment period: starts at first dosing date/time on Study Day 1 and lasts in each study part.

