# 10 CHANGES TO THE STATISTICAL ANALYSES SECTION OF THE PROTOCOL

The statistical analysis of the secondary imaging endpoint will be carried out for the Response-Evaluable 2 population. The protocol erroneously refers to the Response-Evaluable 1 population here, however, this subset would apply to endpoints based on whole body scan data, not cranial scan data.

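### Do the AE tables need to cover non-serious events that start between arterial line insertion and the first tracer dose?

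*SAP*

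**What the plan says.** SAP section 7.6.2 sets the start of the window: "Treatment-emergent adverse events (TEAEs) will be defined as any AEs that start on or after administration of study treatment". It closes 10 days after the last dose or at the last visit, whichever is later. The section adds "Only TEAEs will be tabulated". SAP section 6.1 works to the clock time: "On treatment period: starts at first dosing date/time on Study Day 1". The cut therefore falls within Day 1. Section 7.6.2 also provides a listing of every recorded AE for the Enrolled population, and section 7.6.3 summarises all reported SAEs without a treatment-emergent limit.

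Protocol Table 10.4.2-1 gives the AE endpoint the timeframe "Treatment emergent during the study". The text below that table says "All recorded AEs will be listed according to system organ class and preferred term and tabulated by study part". SAP section 10 records one departure from the protocol, which begins "The statistical analysis of the secondary imaging endpoint will be carried out"; it does not mention AE tables.

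The schedules fix the order of events. The row for "arterial line placement" is marked at Visit 2 only in Table 2-2 (Part A) and at Visits 1 and 2 in Table 2-3 (Part B), each time ahead of that visit's tracer. Table 2-2 also says "The cranial PET scan is performed after the whole-body PET-CT scan", so the main Part A participants have already had a tracer dose when the line goes in. The up to 2 added Part A participants have Visit 2 only, counted as their Day 1. Footnotes to both tables allow one line to serve two same-day scans.

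**The concern.** Protocol section 3.3 names pain, bruising, bleeding and haematoma among the risks of the arterial catheter, and some of these would start at insertion. The treatment-emergent rule seems to count them in one group and drop them in another, purely because of where the first tracer falls. AE incidence is a primary endpoint, and SAP section 7.1 says the by-part summaries are meant to let healthy participants be compared with participants with MS. If the Part B column left out insertion events that the Part A column included, catheter-related events would look rarer in MS than they were.

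There is also a mismatch of wording. The protocol text speaks of tabulating all recorded AEs by part, the SAP tabulates only treatment-emergent ones, and SAP section 10 does not list this as a change.

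**Working it through.** The plan states no figure on this point, so the check is of event order and counts. Planned maximum numbers are used, with no repeat scans.

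**Inputs.** Main Part A 6, added Part A 2 and Part B 8, total 16 (protocol section 5.1). Line timing is from Tables 2-2 and 2-3.

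**1. Order of first line and first tracer.**
- Main Part A: line after first tracer, 6 of 6 on the Table 2-2 grid.
- Added Part A: line before the only planned tracer, 2 of 2.
- Part B: first line before first tracer, 8 of 8.

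Participants whose first line precedes first tracer: 2 + 8 = 10 of 16 = 62.5%. If main Part A participants also had a line in place before a same-day first scan, which the Table 2-2 footnote leaves open, this could be as many as 16 of 16. Main Part A would then lose the same interval as Part B.

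**2. Insertions affected.** With separate lines at both Part B visits, total insertions are 6 + 2 + 16 = 24, and 10/24 = 41.7% precede first tracer. If every Part B participant reuses one line, the total is 6 + 2 + 8 = 16, and 10/16 = 62.5%.

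**3. Does this unbalance the columns?** Call an insertion fully counted if the time from insertion to that scan's tracer lies wholly inside the tabulated window.
- Main Part A: 6/6 = 1.00 per participant.
- Added Part A: 0/2 = 0.
- Whole Part A column: 6/8 = 0.75.
- Part B, with m of 8 participants reusing one line: (8 − m)/8. This is 1.00 at m = 0, 0.75 at m = 2 and 0 at m = 8.

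Part B equals main Part A at m = 0 and the whole Part A column at m = 2. At m = 0 it exceeds the whole Part A column; above m = 2 it falls below. The documents do not give m, so the sign of any imbalance is unknown.

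**4. Size of one event.** 1/8 = 12.5 percentage points in a Part B row and 1/16 = 6.25 in the overall column. These are simply the steps in which percentages move at this sample size.

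**5. Chance of any such event.** The documents give rates only for major or permanent catheter complications, not for minor ones in this short interval. Assume, for illustration, a probability p per insertion, independent across the 10 pre-tracer insertions. The chance of at least one is 1 − (1 − p)^10:

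| Assumed p | At least one in 10 |
|---|---|
| 1% | 9.6% |
| 5% | 40.1% |
| 10% | 65.1% |
| 20% | 89.3% |

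So such an event may or may not occur. If it is recorded as a non-serious AE, it appears in the listing.

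**6. Would it be recorded as an AE?** Protocol section 9.2.3 requires identified non-serious AEs to go on the AE page. Section 9.2.1 sends occurrences after consent but before study intervention to a CRF section it does not name, and Appendix 3 defines an AE in a participant who has been given study treatment. The documents therefore do not settle whether a pre-tracer haematoma reaches the AE page. They also show no recorded insertion time or line count.

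**The case for a change.** The best case for a change is that it would be cheap and that the gap is real. Table 2-3 calls for circulation checks after the line is placed and for non-serious AE assessment at Visit 1, so staff are looking for events in just this interval. Tracer times are in the CRF, and onset time is already used in the SAP's rule for selecting among repeated events. One small supplementary table and one sentence in section 10 would show insertion events on the same footing in each group.

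Some of this stands. Non-serious events that start before the first tracer are outside the tables, and section 10 does not comment on the protocol's sentence about tabulating all recorded AEs. The SAP also imputes missing AE dates but not times, so a Day 1 event without an onset time has no stated rule.

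The rest is weaker. A table with insertions as its denominator needs placement data that the documents do not show being collected. Choosing events by AE term afterwards is a matter of judgement. Parts A and B also differ in catheter exposure by design, one scheduled line against two, so their columns were never a like-for-like measure of cannulation risk. The primary safety objective concerns the tracer and, in Part C, the unlabelled drug.

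**Conclusion.** No change to the plan is needed. Starting the tables at the first tracer follows the protocol's own endpoint timeframe, and treatment-emergent tabulation backed by a full listing is ordinary practice. The events left out are non-serious ones in the short interval from insertion to first tracer, in 10 of 16 planned participants on the schedule grid. Events that start during or after the first scan, while still inside the TEAE window, are tabulated in both parts, and SAEs are summarised whenever they start. With about 16 participants and a synoptic report, a reader can find a listed event by eye.

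The apparent imbalance between parts has no established sign: it disappears against main Part A when Part B lines are separate, and it depends on line reuse that the documents do not report. The missing sentence in SAP section 10 is a documentation slip. The protocol's endpoint table already resolves it in favour of treatment-emergent events, and adding the sentence would alter no result.

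This conclusion assumes planned numbers, no repeat scans and line timing as shown in Tables 2-2 and 2-3. That these events appear in the listing also assumes they are entered as AEs. If they are not, the supplementary table would miss them too.

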#### AE counting rule:

Where a participant has the same adverse event, based on preferred terminology, reported multiple times in a single analysis period, the participant will only be counted once at the preferred terminology level in adverse event frequency tables.

Where a participant has multiple adverse events within the same system organ class in a single analysis period, the participant will only be counted once at the system organ class level in adverse event frequency tables.

When a participant has the same adverse event, based on preferred terminology, reported multiple times in a single analysis period, the following criteria, in order of precedence, will be used to select the event to be included in summary tables:

- Relationship to study medication
- Severity/Intensity of event
- Onset date and time

When reporting adverse events by intensity, in addition to providing a summary table based on the event selection criteria detailed above, summary tables will also be provided based on the most intense event during the analysis period - independent of relationship to study medication. For these tables, the following criteria, in order of precedence, will be used to select the event to be included in summary tables:

- Severity/Intensity of event
- Onset date and time

Listings of all recorded AEs will be provided for the Enrolled population.

#### 7.6.3 Serious Adverse Events

All reported serious adverse events (SAEs) if any will be summarized by SOC, PT, treatment, and overall.

## 7.6.4 Clinical Laboratory Evaluations

A listing of pregnancy test results will be created.

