## 4 ENDPOINTS

The study endpoints are summarized in Table 4-1.

Table 4-1: Objectives and Endpoints

Objectives		Endpoints
Primary	To assess safety, tolerability, kinetics, and CNS signal repeatability of the novel tracer  C-BMS-986196 in healthy participants and in participants with MS	Incidence, severity, seriousness, and type of AEs; clinically significant abnormalities in ECG, VS, laboratory values, physical examination, and C-SSRS
		• Radiation dosimetry calculated from PET-CT images in healthy participants
		
 
Image acquisition window after administration of C-BMS-986196
 

		• Test-retest repeatability based on quantitative analysis of CNS PET-MRI images (eg, SUV and/or V T ) in participants with MS
		• % Free brain BTK relative to baseline
Secondary	To assess  C-BMS-986196 signal characterization	Calculated SUV and V T in the brain

Table 4-1: Objectives and Endpoints

Abbreviations: AE, adverse event; BTK, Bruton's tyrosine kinase; CNS, central nervous system; C-SSRS, Columbia-Suicide Severity Rating Scale; ECG, electrocardiogram;

MS, multiple sclerosis; PET, positron emission tomography; PET-CT, positron emission tomography - magnetic resonance imaging;

SUV, standardized uptake value; VS, vital signs; VT, volume of distribution.

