#### 7.6.5 ECG

Summary statistics will be presented for each ECG parameter (heart rate, PR interval, QRS duration, QT interval, QTcF interval) and the corresponding changes from baseline by visit and time-point, for each study part.

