#### 7.6.6 Vital Signs and Physical Measurements

Not applicable.

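### The SAP plans no output for laboratory results (other than pregnancy tests) or vital signs, although the protocol makes both part of a primary endpoint and promises summaries; SAP Section 10 does not declare the change

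*SAP*

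**What the plan says.** **Protocol.** Table 10.4.2-1 gives a primary endpoint for the Safety population, in a row separate from the adverse event (AE) endpoint: "Incidence of clinically significant abnormal findings in ECG, laboratory values, VS, physical examination". The text under the table adds three commitments:

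- "Clinical laboratory test results as reported on Lab CRF will be reported separately"
- "Vital signs as reported on the VS CRF will be reported separately"
- "Vital signs, ECGs, and laboratory test results will be summarized"

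Protocol Tables 2-2 and 2-3 schedule haematology, chemistry, urinalysis and vital signs at the PET visits of Parts A and B.

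**SAP.** Table 4-1 keeps the endpoint as primary: "clinically significant abnormalities in ECG, VS, laboratory values, physical examination, and C-SSRS". The C-SSRS component belongs to Part C only, and the note at the head of SAP Section 6 restricts the later sections to Parts A and B. Section 7.6.4 (laboratory) consists of one sentence: "A listing of pregnancy test results will be created". The section headed "7.6.6 Vital Signs and Physical Measurements" says only that it is not applicable. Section 7.6.5, by contrast, plans an ECG analysis: "Summary statistics will be presented for each ECG parameter (heart rate, PR interval, QRS duration, QT interval, QTcF interval", with changes from baseline, by visit and time-point. Section 7.6.7 counts participants with an abnormal physical examination. Section 10 records a single departure from the protocol, the population for the secondary imaging endpoint.

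**The concern.** A primary endpoint that the SAP itself restates has two components with no analysis behind them, and a reader of the SAP is not told that anything was dropped. If the report follows the SAP as written, laboratory and vital-sign results collected around each tracer administration, in the first human study of this tracer, would have no planned table or listing beyond pregnancy tests.

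Two things are at stake. One is the incidence of clinically significant findings by component, which the protocol names as an endpoint in its own right. The other is the plain description of the results. For example, Protocol Table 3.3.1-1 lists amylase, lipase and glucose testing among its mitigations for the pancreatic risk. The protocol regards that risk as rat-specific, but these values would still have no planned output.

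**Working it through.** There is no figure to recompute: the study has no hypotheses and no power-based sample size. The check sets the protocol's commitments against the SAP sections, component by component, for Parts A and B.

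| Component (Protocol Table 10.4.2-1) | Data collected at PET visits | SAP section | Output of results planned |
|---|---|---|---|
| Laboratory values | Yes | 7.6.4 | Pregnancy-test listing only |
| Vital signs | Yes | 7.6.6 | None |
| ECG | Yes | 7.6.5 | Parameter summaries by visit and time-point |
| Physical examination | Yes | 7.6.7 | Count of abnormal examinations by visit |

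Components with no output of results, pregnancy tests aside: 4 − 2 = 2 of 4.

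**Is the omission declared?** Section 10 declares one change, on another subject. The Section 6 note on early termination limits the scope to Parts A and B and announces a synoptic report, but does not withdraw these analyses. Where the SAP leaves out other primary endpoints (dosimetry and the acquisition window), Sections 7.5 and 7.5.1 say so and name the imaging report as the place where they will appear. Laboratory and vital-sign results get no such statement.

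**Does another route supply the endpoint?** In part:

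1. Protocol Section 9.2.6 sends clinically significant laboratory results to the AE record. Section 9.4.5 does so for ECGs. Section 9.2.8 covers significant worsening on physical examination, ECG or any other safety assessment. Appendix 3 treats clinically significant laboratory, ECG and vital-sign results as AEs.
2. SAP Section 7.6.2 tabulates treatment-emergent AEs with the Safety population as denominator and lists every recorded AE.
3. Those tables group events by system organ class and preferred term, not by the assessment that produced the finding. Under Appendix 3 an abnormal result is renamed once a diagnosis is known. A component-specific count therefore cannot always be rebuilt from them.
4. AE tables contain no summary of measured values, so they cannot meet the commitment to summarize results.

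**Could unseen material supply it?** The Data Presentation Plan mentioned in SAP Section 9 is not among the documents. It could add outputs, but Section 9 rests the report's statistics on the SAP's own content. The SAP contents list also has a blank, apparently redacted, entry after 7.6.8. Laboratory results and vital signs have their own visible headings, so that entry is unlikely to hold them.

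**The case against.** The strongest reply is that little of practical weight is missing. The tracer mass is at most 20 µg and is described as not pharmacologically relevant. Planned enrolment in Parts A and B is 8 + 8 = 16. No serious or severe AE had been reported by 21-Mar-2023. The study was stopped early and will have a synoptic report. Medical history, concomitant medication and Allen's test are also marked not applicable in the SAP, which suggests deliberate trimming. Clinically significant findings reach the AE tables in any case, and with so few participants the AE listing can be read case by case.

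Most of this stands, and it limits the weight of the point. It does not remove it. The other trimmed items are not components of a primary endpoint, and the SAP nowhere says that this endpoint will be met through AEs. A shorter report is a reasonable choice, but the change needs to be declared.

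A reader might infer that clinically significant laboratory and vital-sign findings will go unreported. The documents do not support that, because the AE route covers them. A reader might also infer that the whole four-component endpoint lacks analysis, since the ECG and physical-examination sections do not count clinically significant findings either. That goes too far: Section 7.6.5 delivers the ECG summary that the protocol promised, and Section 7.6.7 counts a broader category of abnormal examinations. Adding a clinically significant count to those two sections is optional.

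**Conclusion.** The point holds as an undeclared departure from the protocol on a primary safety endpoint. Two of the four applicable components have no planned output of results in the visible SAP, apart from pregnancy tests. The loss is the component-specific incidence and the promised descriptive summaries, not all reporting.

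It should be corrected, at modest priority: it is partly offset by AE reporting, it affects descriptive output only, and it is cheap to repair. Confidence is high that the SAP text omits these analyses. It is lower on what the final report will lack, because the Data Presentation Plan is not available. The documents also do not say whether the case report forms carry a clinical-significance flag.

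**What to change.** In SAP Sections 7.6.4 and 7.6.6, for the Safety population by study part, add:

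1. Descriptive summaries of laboratory results by visit, showing n at each visit. In Part B, same-day scans do not require a duplicate laboratory sample, so such participants may contribute only one.
2. Descriptive summaries of vital signs by visit and time-point, as Section 7.6.5 does for ECG. Readings are taken before tracer, after the scan and before discharge, so a summary by visit alone would mix them. Protocol Section 9.4.3 allows the discharge reading to be sitting or supine, which a footnote should state.
3. The number and percentage of participants with a treatment-emergent clinically significant laboratory finding, and likewise for vital signs. Use the case report form flag if there is one. Otherwise use the AE record, with a footnote that events recoded to a diagnosis may be missed.

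Alternatively, declare and justify the omission in SAP Section 10, state that clinically significant findings are captured through AEs, and provide listings of abnormal laboratory and vital-sign values.

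**Cost.** No new data are needed, only a small amount of programming. Protocol Table 9.4.6-1 has 4 haematology lines and 21 chemistry lines after Screening (creatinine clearance is Screening only), so 4 + 21 = 25, plus urinalysis. Local laboratories supply their own reference ranges, so units and ranges may need harmonizing across sites. Counts taken from the AE record may be too low, and with so few participants all of the results are descriptive.
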